## SECTION II: GENERAL INFORMATION

1. **Performing Organizations:** Identify the hospital, in-patient or outpatient facility, school or other agency that will serve as the location of the research. Choose all that apply:

a. **Internal Location[s] of the Study:**

	Magnetic Resonance Research Center		Yale University PET Center
	(MR-TAC) YCCI/Church Street		Research Unit (CSRU)
	Yale Cancer Center/Clinical Trials Office		(CTO) YCCI/Hospital Research Unit (HRU)
	Yale Cancer Center/Smilow YCCI/Keck		Laboratories
	Yale-New Haven Hospital Yale-New		Haven Hospital—Saint Raphael Campus
	Cancer Data Repository/Tumor Registry		

Specify Other Yale Location:

b. **External Location[s]:**

	APT Foundation, Inc.	Haskins Laboratories
	Connecticut Mental Health Center	John B. Pierce Laboratory, Inc.
		
		

Clinical Neuroscience Research Unit (CNRU)  Veterans Affairs Hospital, West Haven  Other Locations, Specify: SATU International Research Site

(Specify location(s)):

**c. Additional Required Documents (check all that apply):**  N/A

\*YCCI-Scientific and Safety Committee (YCCI-SSC) Approval Date:

\*Pediatric Protocol Review Committee (PPRC) Approval Date: \*YCC

Protocol Review Committee (YRC-PRC) Approval Date:

\*Dept. of Veterans Affairs, West Haven VA HSS Approval Date: \*Radioactive

Drug Research Committee (RDRC) Approval Date:

YNHH-Radiation Safety Committee (YNHH-RSC) Approval Date:

Yale University RSC (YU-RSC) Approval Date: Magnetic Resonance Research

Center PRC (MRRC-PRC) Approval Date: \*Nursing Research Committee

Approval Date:

YSM/YNHH Cancer Data Repository (CaDR) Approval Date:

Dept. of Lab Medicine request for services or specimens form

Imaging on YNHH Diagnostic Radiology equipment request form (YDRCTO request) found at

<http://radiology.yale.edu/research/ClinTrials.aspx>

**\*Approval from these committees is required before final HIC approval is granted. See instructions for documents required for initial submission and approval of the protocol. Allow sufficient time for these requests. Check with the oversight body for their time requirements.**

**2. Probable Duration of Project:** State the expected duration of the project, including all followup and data analysis activities. 3 years

**3. Research Type/Phase: (Check all that apply)**

**a. Study Type**

Single Center Study

Multi-Center Study

Does the Yale PI serve as the PI of the multi-site study? Yes  No

Coordinating Center/Data Management Other:

**b. Study Phase**  N/A

Pilot  Phase I  Phase II  Phase III  Phase IV

Other (Specify)

**4. Area of Research: (Check all that apply)** Note that these are overlapping definitions and more than one category may apply to your research protocol. Definitions for the following can be found in the instructions section 4c:

Clinical Research: Patient-Oriented

Clinical Research: Outcomes and

Clinical Research: Epidemiologic and Behavioral

Health Services

Translational Research #1 ("Bench-to-

Bedside") Interdisciplinary

Research

Translational Research #2 (“Bedside-to-Community”) Community-Based Research 5. Is this study a clinical trial? Yes  No

*NOTE the current ICMJE (International Committee of Medical Journal Editors) definition of a clinical trial: “any research study that prospectively assigns human participants or groups of humans to one or more health-related interventions to evaluate the effects on health outcomes.” Health-related interventions include any intervention used to modify a biomedical or health-related outcome (for example, drugs, surgical procedures, devices, behavioral treatments, dietary interventions, and process-of-care changes). Health outcomes include any biomedical or health-related measures obtained in patients or participants, including pharmacokinetic measures and adverse events”* If yes, where is it registered?

Clinical Trials.gov registry   
Other (Specify)

Registration of clinical trials at their initiation is required by the FDA, NIH and by the ICMJE.

For more information on registering clinical trials, including whether your trial must be registered, see the YCCI webpage, <http://ycci.yale.edu/researchers/ors/registerstudy.aspx> or contact YCCI at [contact])

1. Does the Clinical Trials Agreement (CTA) require compliance with ICH GCP (E6)?  
Yes  No

7. Will this study have a billable service? *A billable service is defined as any service rendered to a study subject that, if he/she was not on a study, would normally generate a bill from either YaleNew Haven Hospital or Yale Medical Group to the patient or the patient's insurer. The service may or may not be performed by the research staff on your study, but may be provided by professionals within either Yale-New Haven Hospital or Yale Medical Group (examples include x-rays, MRIs, CT scans, specimens sent to central labs, or specimens sent to pathology). Notes: 1. There is no distinction made whether the service is paid for by the subject or their insurance (Standard of Care) or by the study's funding mechanism (Research Sponsored). 2. This generally includes new services or orders placed in EPIC for research subjects.*

Yes  No

If answered, “yes”, this study will need to be set up in OnCore, Yale’s clinical research management system, for Epic to appropriately route research related charges. Please contact [[contact]](mailto:[contact])

8. Are there any procedures involved in this protocol that will be performed at YNHH or one of its affiliated entities? Yes X No \_\_\_ If Yes, please answer questions a through c and note instructions below. If No, proceed to Section III.

a. Does your YNHH privilege delineation currently include the **specific procedure** that you will perform? Yes

b. Will you be using any new equipment or equipment that you have not used in the past for this procedure? No

c. Will a novel approach using existing equipment be applied? No

If you answered "no" to question 8a, or "yes" to question 8b or c, please contact the YNHH Department of Physician Services ([name]) for prior approval before commencing with your research protocol.

*Please note that if this protocol includes Yale-New Haven Hospital patients, including patients at the HRU, the Principal Investigator and any co-investigators who are physicians or mid-level practitioners (includes PAs, APRNs, psychologists and speech pathologists) who may have direct patient contact with patients on YNHH premises must have medical staff appointment and appropriate clinical privileges at YNHH. If you are uncertain whether the study personnel meet the criteria, please telephone the Physician Services Department at [contact]. By signing this protocol as a PI, you attest that you and any co-investigator who may have patient contact has a medical staff appointment and appropriate clinical privileges at YNHH.*

### SECTION III: FUNDING, RESEARCH TEAM AND TRAINING

1. **Funding Source:** Indicate all of the funding source(s) for this study. Check all boxes that apply. Provide information regarding the external funding source. This information should include identification of the agency/sponsor, the funding mechanism (grant or contract), and whether the award is pending or has been awarded. Provide the M/C# and Agency name (if grantfunded). If the funding source associated with a protocol is "pending" at the time of the protocol submission to the HIC (as is the case for most NIH submissions), the PI should note "Pending" in the appropriate section of the protocol application, provide the M/C# and Agency name (if grant-funded) and further note that University (departmental) funds support the research (until such time that an award is made).

PI	Title of Grant	Name of Funding Source	Funding	Funding Mechanism
[name] (Center PI); [name] (Project PI)	Center for Translational Neuroscience on Alcoholism	NIAAA	 Federal  State  Non Profit  Industry  Other For Profit  Other	 Grant-M# P50AA12870  Contract#  Contract Pending  Investigator/Department Initiated  Sponsor Initiated  Other, Specify:

IRB Review fees are charged for projects funded by Industry or Other For-Profit Sponsors. Provide the Name and Address of the Sponsor Representative to whom the invoice should be sent. **Note:** *the PI's home department will be billed if this information is not provided.*

## SECTION V: RESEARCH PLAN

1. **Statement of Purpose:** State the scientific aim(s) of the study, or the hypotheses to be tested. Alcoholism is a disorder that is mediated by multiple genes and environmental factors. Existing medications like naltrexone and acamprosate are not efficacious in all drinkers. Therefore, we need to develop new and effective strategies to treat alcoholism. Development of medications for this disorder should be based on our understanding of the behavioral and neurochemical mechanisms mediating alcohol reward and drinking. There is extensive preclinical evidence suggesting that glutamatergic circuits are involved in the acute behavioral effects of alcohol as well as in alcohol tolerance and withdrawal. This project will evaluate the effect of an agent that indirectly modulates NMDA-R signaling without directly antagonizing NMDA-Rs on alcohol drinking. Specifically, we will test the influence of Saracatinib, a Src/Fyn protein tyrosine kinase inhibitor that modulates NMDA-R signaling via Fyn inhibition.

**Primary Aim 1:** To evaluate the effects of Saracatinib (125 mg/day) versus placebo on alcohol craving.

*Primary hypothesis 1a:* Saracatinib (125 mg/day) will reduce craving for alcohol after exposure to the priming drink of alcohol, and during the free-choice drinking period, when compared with placebo.

**Primary Aim 2:** To evaluate the effects Saracatinib (125 mg/day) versus placebo on alcohol drinking

*Primary hypothesis 1b:* Saracatinib (125 mg/day) will reduce number of drinks consumed during the free-choice drinking period, when compared with placebo.

**Secondary Aim 1:** To evaluate the effects of Saracatinib (125 mg/day), versus placebo, on alcohol-induced stimulation and sedation during the ADP.

**Secondary Aim 2:** To examine the tolerability of Saracatinib (125 mg/day) in heavy drinkers.

**Exploratory Aims:** To explore predictors of Saracatinib response. The predictors have been selected based on findings from our earlier work and include behavioral outcomes like impulsivity, habit and deficiency in loss-avoidance learning, genetic markers related to alcohol drinking or glutamate and Src/Fyn systems, and neural networks/markers identified using multimodal neuroimaging.

2. **Background:** Describe the background information that led to the plan for this project. Provide references to support the expectation of obtaining useful scientific data.

This novel project will conduct the first test of whether human alcohol consumption may be altered by targeting an intracellular signaling protein implicated in alcohol dependence, Fyn kinase.

Alcohol-seeking behaviors involve complex interactions between neurotransmitters like dopamine and opioids that underlie reward in the nucleus accumbens and engage habits in the dorsal striatum, and glutamatergic pathways from the prefrontal cortex and basolateral amygdala to the nucleus accumbens that are involved in the reinstatement of alcohol drinking (e.g. Koob and Volkow, 2010).

Using the alcohol drinking paradigm (ADP) that is being used in the current study, we showed in our earlier studies that naltrexone reduced drinking in FHP heavy drinkers ([name] et al., 2007) but did not reduce alcohol craving. In subsequent studies we observed that a low dose (20 mg) of the NMDA receptor (NMDA-R) antagonist, memantine, reduced alcohol craving, but not drinking ([name] et al., in press). Further, the higher dose of memantine (40 mg) reduced alcohol craving, but increased drinking and alcohol-induced stimulation among those who were more behaviorally impulsive. Therefore, we hypothesized that a more nuanced approach of altering NMDA-R signaling, that reduces alcohol drinking and craving without increasing positive alcohol effects, might be needed. In an ongoing project, we are studying the potential synergy of low dose memantine (which reduced craving) with 50 mg naltrexone (which reduced drinking; HIC protocol 1005006779). In this project, we propose to examine the effects of an agent that indirectly modulates NMDA-R signaling without directly antagonizing NMDA-Rs. Specifically, we will test the influence of Saracatinib on drinking behaviors.

Saracatinib is a Src/Fyn protein tyrosine kinase inhibitor that modulates NMDA-R signaling via Fyn inhibition. Importantly, this agent could target pathways in the corticostriatal circuitry where NMDA-upregulation may emerge as a consequence of heritable or alcohol-induced (Martinez et al 2005) reductions in dopamine D2 receptor signaling and subsequent upregulation of Fyn (Hattori et al 2006). Saracatinib or AZD0530 is an inhibitor of Src Family kinases, blocking Src, Fyn, Yes and Lyn, with 2- 10 nM potency. At 10-100 fold higher concentrations the compound also inhibits Abl family kinases, but there is no detectable activity in this concentration range against other kinase families, including c-kit, Csk and PDGFR. An in vitro screen of AZD0530 against 307 different pharmacological targets, showed  $\geq 50\%$  inhibition of binding or function of only 9 targets at 10  $\mu\text{M}$  and one additional enzyme at 100  $\mu\text{M}$  (unpublished data from Astra Zeneca). It is estimated that the IC50 values for all 10 non-SFK targets are likely to be in the region of at least 3-100  $\mu\text{M}$  (compared to a Fyn IC50 of 0.005  $\mu\text{M}$ ), and so any inhibition is unlikely to be clinically significant.

AZD0530's specific inhibition of Fyn and SFKs have led to its development as therapy for solid tumors, because Src family kinases regulate tumor cell adhesion, migration and invasion, and also regulate proliferation. Clinical tolerability and oral bioavailability have been demonstrated, but Phase II studies have demonstrated limited benefit as a single agent in specific oncological indications. For tumor cell migration and for oncological applications, it is estimated that  $>98\%$  kinase inhibition is required so clinical doses have targeted concentrations  $>20$ -fold above the kinase IC50, in the 200-1000 nM concentration. Saracatinib has been studied in healthy individuals and patients with solid tumors (Dalton et al., 2010; Baselga et al., 2010; Fujisaka et al., 2013; Hannon et al., 2012) and in older patients with mild-moderate Alzheimers disease. [name] and colleagues from Yale recently conducted a 4-week Phase Ib multiple ascending dose, randomized, double-blind, placebo-controlled trial of AZD0530 in AD patients with Mini-Mental State Examination (MMSE) scores ranging from 16 to 26 ([name] et al., 2015). They observed that the 100 and 125 m doses of AZD were generally safe and well tolerated that these doses achieved CSF drug levels corresponding to brain levels that rescued memory deficits in transgenic mouse models. Moreover, one-month treatment with AZD0530 had no significant effect on clinical efficacy measures or regional cerebral glucose metabolism.

We recently completed a pilot study to evaluate the preliminary safety, tolerability and effects of the combined administration of AZD0530 (125 mg/day) and alcohol (HIC# 0602001068). Five heavy

social drinkers (mean age = 26 ± 2.2) completed a baseline inpatient alcohol administration session and a second alcohol administration session after taking AZD0530 for 8 days (to reach steady state levels). During each alcohol administration session, subjects received successive doses of alcohol designed to raise their blood alcohol levels to 80 mg/dl. We observed the drug was safe and tolerable over the 8-day outpatient administration period. Only mild adverse events were reported by two subjects and no other adverse events were reported. Complete blood counts and serum chemistries were similar across all pre- and post- drug and alcohol time points, with all values within the appropriate reference range, with only glucose and calcium slightly elevated. As expected, given the acute effects of alcohol, changes in heart rate and systolic blood pressure were seen within each drinking session, as were changes in blood alcohol levels and urine alcohol levels. No session related differences were observed indicating no effect of AZD0530 on these parameters. Furthermore, the results of the cognitive measures suggest that AZD0530 does not have an independent effect on cognitive performance or in combination with alcohol, but that alcohol affects these measures as expected. We also observed a promising signal on the alcohol intoxication assessment (reduced stimulation, intoxication, feel good drug effects) following exposure to alcohol. Thus, this study of 125 mg of AZD0530 given to healthy social drinking controls over 8 days in an alcohol administration session, raising blood alcohol to 80 mg/dl, did not result in any concerning changes in physiological or behavioral outcome measures and showed some promise for reducing alcohol related positive effects after exposure to alcohol.

[figure not shown]
The current proof-of-concept trial will test the effects of 125 mg dose of Saracatinib versus placebo on alcohol drinking behaviors using the ADP. We have determined that there is a need to focus on the 125 mg dose and that there is no advantage to testing a lower dose (50 mg) of the drug as proposed in the grant. The 50 mg dose is known to be inferior to the 125 mg in terms of Src family target coverage both peripherally and centrally and therefore the pharmacologic effect of the 50 mg dose should not be superior to the 125 mg dose. In addition, this will also allow Astra Zeneca to provide us with the 125 mg and matching placebo over a 3-year period without having to conduct additional stability testing over an extended period of time. Therefore, with the goal of getting this proof of principle trial done in an efficient manner, we will now focus on an adequately powered examination of the 125 mg dose, the dose we believe will be effective based on our preliminary data and knowledge of target engagement. Specifically, in the first three years of the grant, we will recruit 60 subjects and randomize 40 subjects to the 125 mg Saracatinib dose and 20 subjects to placebo. We anticipate a 10% drop out, leaving a final sample of 50 completers.

Thus, 60 non-treatment seeking, heavy drinkers will receive Saracatinib (0 or 125 mg/day), stratified by gender(to achieve 50 completers). Subjects will participate in a baseline ADP, followed by seven days of treatment with the study medication, and then a second ADP when they will take their last dose of study medication. Drinking behavior, alcohol craving and alcohol-induced stimulation/sedation will be measured in each ADP. Adverse events and drinking will be monitored during the treatment period, and at follow up. Potential behavioral predictors of Saracatinib response will be obtained at baseline and post-treatment ADP, and the CTNA core assessment battery will be obtained at baseline.

2. **Research Plan:** Summarize the study design and research procedures using non-technical language that can be readily understood by someone outside the discipline. **Be sure to distinguish between standard of care vs. research procedures when applicable, and include any flowcharts of visits specifying their individual times and lengths.** Describe the setting in which the research will take place.

A between subjects design will be used to examine the effects of Saracatinib on alcohol craving, drinking and subjective responses in heavy drinkers. Non-treatment seeking heavy drinkers will

participate in two ADP sessions, occurring prior to and after eight days of medication treatment, and will complete one-week and 1-month follow up appointments (see below).

60 heavy drinkers, drinking on at least 4 days per week (20-65 weekly standard drinks for women and 30-70 for men) will complete this study. All subjects will be 21-50 years of age, physically healthy non-treatment-seeking heavy drinkers. Volunteers will be recruited through advertisements in local newspapers, postings in community locations (bars, coffee shops, grocery stores) and advertisements on free community TV channels. Subjects who do not meet the inclusion/exclusion criteria described below will be excluded.

The study will consist of six phases: 1) recruit subjects, obtain informed consent and evaluate eligibility for the study, 2) potentially eligible subjects will then receive a full physical examination to further determine eligibility. 3) If eligible they will participate in the baseline ADP in the Hospital Research Unit (HRU) of Yale New Haven hospital (YNHH), 4) they will be randomized to receive 0 mg or 125 mg/day of Saracatinib for a 7-10 day outpatient medication treatment period (depending on ADP scheduling) with daily medication/adverse event recording appts 5) they will complete the second ADP on the last medication day in the Hospital Research Unit (HRU) of Yale New Haven hospital (YNHH), after taking the last dose of study medication, 6) they will be scheduled for one-week and one-month follow up appointments. At the one week follow up, adverse events and drinking will be recorded and a clinical psychologist or social worker will provide a motivational enhancement session to motivate these non-treatment seeking drinkers to consider treatment. They will also be given the option to participate in an fMRI at the one-month follow-up appointment.

**Justification for choice of Saracatinib dose:** Saracatinib has been extensively studied in healthy individuals and patients with solid tumors (Dalton et al., 2010; Baselga et al., 2010; Fujisaka et al., 2013; Hannon et al., 2012) and more recently in patients with Alzheimers disease. For our “proof-of-concept” trial, we chose to use a higher dose of 125 mg, which have most commonly been tested in most trials (including those by our collaborator [name] with AD patients) and shown to be safe. AZ has completed 7 Phase I studies in healthy volunteers and 5 Phase I studies in patients with solid tumors and advanced solid malignancies. AZD0530 doses of 60 mg to 185 mg were well tolerated, and although adverse events were more frequent at and above 250 mg, no major safety issues were identified at any of the doses studied. In patients with advanced cancer, the MTD was 175mg. In clinical oncology, the duration of AZD0530 treatment has been 2-12+ weeks in most trials. Importantly, with AZD0530 monotherapy no serious hematologic adverse events have been documented in doses lower than 175 mg. In the phase 1 trials, no major safety issues were identified in any of the doses studied, up to 250 mg daily. There is a potential for mild decreases in values for both white cell count and platelets at doses of above 125 mg, but these abnormalities never fell below reference levels, and levels normalized while patients remained on the drug. Thus, the dose proposed in this study, 125 mg, has not only been used safely in healthy volunteers and patients with cancer and AD, but have also been used for longer periods than the six days proposed in the current project.

We have completed a pilot trial (HIC # 0602001068) to examine if there are any interactions between AZD0530 (at the highest dose proposed in the current project i.e. 125 mg/day) and a moderate dose of alcohol (0.08 mg/dl; similar to the blood alcohol levels usually achieved by drinkers in our ADP paradigms) following 8 days of AZD0530 treatment (similar to the current protocol) in social drinkers. Five subjects have participated and no unanticipated adverse effects have been noted; findings were presented to the FDA, and HIC.

**Justification for length of treatment phase:** We chose to study the effect of Saracatinib on alcohol drinking following eight days' pretreatment to allow sufficient drug to accumulate. Per information in the AZ brochure, the PK profile of Saracatinib supports once-daily oral administration, with peak levels seen 3-4 hours after administration, and a mean t1/2 of about 40 hours. This treatment period also allows us to generate clinically relevant information on adverse events observed beyond an acute dose in heavy drinkers.

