**4.b. Frequency of Review of Safety Reports**

Subjects are recruited at a maximum rate of 2 per month; thus, the DSMB will review safety reports two times a year. More frequent meetings will be scheduled if indicated by interim findings.

- d. For multi-site studies for which the Yale PI serves as the lead investigator: N/A
  - i. How will adverse events and unanticipated problems involving risks to subjects or others be reported, reviewed and managed?
  - ii. What provisions are in place for management of interim results? iii. What will the multi-site process be for protocol modifications?

**11. Statistical Considerations:** Describe the statistical analyses that support the study design.

**Power Calculations:** We will recruit up to 90 subjects and randomize 40 subjects to the 125 mg Saracatinib dose and 20 subjects to placebo. We will use the number of drinks consumed at the baseline session (5 or less, 6 or more) and gender as stratification variables in the randomization. 6 drinks is half the total number of drinks they are allowed to drink in the self-administration period and will allow the participant to reach a BAC of 0.07 or higher which is the threshold for heavy drinking. We anticipate that we will obtain complete data on 52 subjects in approximately 2:1 ratio on active vs. placebo. This would give us 80% power to detect large effects of drug ( $d=0.8$  or greater) at two-sided alpha level of 0.05. Such an effect size is considered clinically meaningful and is consistent with our pilot data where we observed large effects of the 125 mg dose (administered over eight days) on alcohol-induced stimulation and feeling intoxicated and feeling good (all  $>0.8$ ) following exposure to a fixed dose of alcohol (0.8 mg/kg) in heavy social drinkers. Randomizing more subjects on active drug will allow us to explore relationships between potential predictors (e.g. gender, smoking status) and outcome in the treatment group. Thus, we will be well powered with our proposed sample to detect clinically relevant effects of Saracatinib.

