treatment on alcohol craving in response to the alcohol cue exposure just prior to the start of the drinking session using a similar model. In the above models, treatment will be considered as a categorical predictor but linear and quadratic effects of dose will also be tested. **Aim 2:** Total number of drinks consumed during the ADP will be compared among treatment conditions using linear mixed models as above with treatment (0 mg or 125 mg Saracatinib) as a between-subjects factor and session (baseline, post-treatment) as a within-subject explanatory factor. We anticipate a significant treatment by session interaction owing to reduced drinking following Saracatinib treatment, but not placebo. We will also consider change from baseline as the outcome measure and compare the treatment groups using ANOVA.

**Secondary Aim 1:** Alcohol-induced stimulation and sedation during ADP will be evaluated using the same linear mixed models outlined in Specific Aim 1, with BAES subscale scores as the dependent variables.

**Secondary Aim 2:** Adverse events will be recorded and summarized qualitatively by treatment group. Total and severe adverse event frequencies will be compared between groups using chisquare or Fisher's exact test. Similar to what our collaborators, Drs. [name] and [name] observed among AD subjects (see preliminary data), we anticipate AE profiles of the two active Saracatinib groups will be similar to placebo. Vital signs and blood alcohol levels and plasma Saracatinib levels assessed during the ADP will also be evaluated using linear models to examine alcohol-Saracatinib interactions.

**Exploratory Aims:** All measures (e.g., PST, Habit, genetic markers, neural markers) will be evaluated using the same models outlined in Specific Aim 2.

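### The two statements of the randomisation strata differ, and the Aim 2 test of change, adjusted for neither factor, is somewhat conservative and loses power when drinking correlates weakly between sessions

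*Combined protocol and SAP*

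**What the plan says.** **Strata.** The last paragraph of the Background in Section V describes the 60 subjects as "stratified by gender(to achieve 50 completers". In Section V, item 11, the Power Calculations paragraph uses "the number of drinks consumed at the baseline session (5 or less, 6 or more) and gender as stratification variables in the randomization", and explains the cut: six drinks is half of what is on offer. The Research Plan places the baseline drinking session before randomisation, so the baseline count is available to stratify on.

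**Analysis.** Under Statistical analyses in item 11:
- Aim 1 models craving with treatment, time, session and their interactions. The expected signal is treatment by time by session.
- Aim 2 models total drinks with treatment and "session (baseline, post-treatment) as a within-subject explanatory factor". The expected signal is treatment by session. An ANOVA on change from baseline is also to be considered.
- Secondary Aim 1 reuses the Aim 1 model for stimulation and sedation.

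None of these names gender or the baseline-drinks stratum as a covariate.

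**The concern.** The text gives two descriptions of one allocation rule, and the analysis does not follow either. When arms are balanced on a factor that predicts the analysed outcome, and that factor is left out of the model, the model-based standard error exceeds the true sampling variability. The test then rejects too rarely under the null and has less power than the design could deliver. With about 52 completers, 17 or 18 of them on placebo, a few points of power matter. The question is how far this applies to a test built on change between two sessions.

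**Working it through.** **Inputs from the documents (Section V, item 11).** The plan is to "randomize 40 subjects to the 125 mg Saracatinib dose and 20 subjects to placebo", with "complete data on 52 subjects in approximately 2:1 ratio on active vs. placebo". The claim reads "This would give us 80% power to detect large effects of drug", with d = 0.8, "or greater) at two-sided alpha level of 0.05".

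**Inputs assumed.** The baseline-to-post correlation ρ is 0.3, 0.5 or 0.7. The baseline-drinks cut falls at the median. The true effect is 0.8 single-session SD. The simulations also assume a 0.5 SD gender effect, equal in both sessions.

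**1. The plan's own figure.** For 35:17, √(1/35 + 1/17) = 0.2956 and 0.8/0.2956 = 2.706. The noncentral t with 50 degrees of freedom gives 75.6% power (34:18: 76.8%). The normal approximation gives 77.2% and 78.4%. So the stated 80% is not quite reached at 2:1. That is a separate matter; here it shows only that there is little margin.

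**2. Which terms can matter.** With two sessions, treatment by session is a comparison of the change D = post − baseline. A stratum effect that is equal in both sessions drops out of D. Mixed models fitted to a simulated dataset of 52 confirm this. The treatment-by-session standard error was 0.2716 without strata, with gender, and with gender plus drinks category as main effects. It fell to 0.2643 only with stratum-by-session terms. A second dataset gave 0.3236 in all three cases and 0.303 with those terms.

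**3. What does not cancel.** In single-session SD units, Var(D) = 2(1 − ρ), and the slope of D on baseline is −(1 − ρ). Baseline therefore explains (1 − ρ)²/[2(1 − ρ)] = (1 − ρ)/2 of the variance of D. A median split of a normal variable keeps 2/π = 0.637 of its variance, so the stratum explains R² = 0.637(1 − ρ)/2.

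- SE reported by the unadjusted change test: SE_u = 0.2956·√[2(1 − ρ)]
- True SE when arms are balanced on strata, and SE of the adjusted test: SE_s = SE_u·√(1 − R²)
- SE with ANCOVA on continuous baseline: SE_a = 0.2956·√(1 − ρ²)
- Type I error, unadjusted: two-sided t tail (50 df) beyond 2.009/√(1 − R²)
- Power, unadjusted: Φ[(0.8 − 2.009·SE_u)/SE_s]
- Power, adjusted: Φ[(0.8 − 2.011·SE)/SE], with SE_s or SE_a

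For ρ = 0.3, the unadjusted power is Φ[(0.8 − 0.703)/0.308] = Φ(0.315) = 62%.

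| ρ | R² | SE_u | SE_s | SE_a | Type I, unadjusted | Power, unadjusted | Power, strata on change | Power, ANCOVA |
|---|---|---|---|---|---|---|---|---|
| 0.3 | 0.223 | 0.350 | 0.308 | 0.282 | 2.7% | 62% | 72% | 80% |
| 0.5 | 0.159 | 0.296 | 0.271 | 0.256 | 3.3% | 78% | 83% | 87% |
| 0.7 | 0.095 | 0.229 | 0.218 | 0.211 | 4.0% | 94% | 95% | 96% |

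**4. Simulation.** The runs used 52 subjects and 2:1 allocation within four strata. The ranges below are across separate runs; at 3,000 trials per setting the Monte Carlo error is up to about 0.8 points on type I error and 1.7 on power.

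| ρ | Type I, unadjusted | Power, unadjusted | Power, strata on change | Power, ANCOVA |
|---|---|---|---|---|
| 0.3 | 2.5–2.7% | 64–64.5% | 73% | 79–80% |
| 0.5 | 2.9–4.0% | 77–78% | 82–83% | 86–87% |
| 0.7 | 3.9–4.7% | 94–94.5% | 95–95.6% | 96–96.5% |

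With strata in the change model, type I error was 4.5% to 5.6%. Adding gender alone changed power from 64.5% to 63.8% at ρ = 0.3 and from 77.3% to 77.1% at ρ = 0.5, which is no gain. At ρ = 0.8 the strata raised power only from 98.6% to 99.0%.

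**The case against.** The strongest reply has four parts.

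1. The primary tests are within-subject contrasts, so the textbook rule about omitted strata does not carry over unchanged. This stands: stable stratum effects cancel, and adding strata as main effects would achieve nothing.
2. Baseline drinking is not ignored, because it is the session-one response in the Aim 2 model. This also stands, but only in part: baseline enters as an outcome, not as a predictor of change, and regression to the mean acts through the second route.
3. The loss depends on a correlation the documents do not give, and it shrinks to a point or two at 0.7 and above. This is correct, and it limits the claim.
4. The discrepancy over strata is editorial. The Background is a summary and does not say gender alone, while the statistical section gives the full rule with its cut and rationale. This is a fair reading. The two places should still agree, because analysing as randomised requires one stated rule.

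A reader might infer that all the trial's error bars are too wide, that false positives are inflated, or that the randomisation itself is compromised. The documents support none of these. The excess standard error is shown for change in drinks only, the error is in the conservative direction, and nothing suggests that two rules were operated.

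**Conclusion.** The point holds in a limited form. The strata are described in two ways, and no planned model or ANOVA adjusts for them. For Aim 2 the consequence is a conservative test. Strata acting on change would gain about 9 or 10 points of power at a correlation of 0.3, about 5 at 0.5 and about 1 at 0.7. ANCOVA on continuous baseline drinks would gain about 15 to 18, 9 and 2 points. Almost all of this comes from baseline drinks.

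These sizes rest on the assumed correlation, approximate normality, a cut near the median and an effect of 0.8 single-session SD. A cut far from the median would lower the share explained by the stratum, but would not affect the continuous-baseline ANCOVA in the same way.

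For Aim 1 and Secondary Aim 1 the gain should be smaller, and the documents do not allow it to be sized. The stratum is defined on drinks, not on craving or stimulation. It would also have to alter the time course differently in the two sessions to bear on the three-way interaction.

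**What to change.** - In the Background of Section V, state the same two-factor rule as in item 11: gender and baseline-session drinks, 5 or less versus 6 or more.
- For Aim 2, prespecify an ANCOVA of post-treatment drinks on treatment, continuous baseline drinks and gender, in place of the unadjusted change-score ANOVA. Alternatively, add gender-by-session and drinks-stratum-by-session terms to the mixed model. State before unblinding which analysis is primary.
- For Aim 1 and Secondary Aim 1, add stratum-by-session terms. Strata as main effects alone leave the interaction tests unchanged. These terms serve the treatment-by-session comparison, and less gain should be expected than in Aim 2.

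The cost is wording in the analysis plan and about two degrees of freedom (50 to 48 in the Aim 2 change comparison). No extra subjects or data are needed.
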